### Test of assumptions

The normality assumption of ANCOVA will be assessed through the Shapiro-Wilk test. Another important assumption of ANCOVA is that the relationship between the dependent factor and the covariate for each subgroup are the same. The regression slope of response factor on the covariate at each subgroup will be tested for equality. The Levene's test will be implemented to test the assumption of homogeneity of regression slope of response factor on the covariate at each subgroup.

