### **Group Comparisons**

At each post-surgery visit, the patient reported outcome (PROMIS, AOS and FAOS) score and the change from baseline scores will be analyzed. Analysis of covariance (ANCOVA) with baseline score as a covariate factor will be implemented for all comparisons (i.e., comparison by disease diagnosis). The components of the ANCOVA model are: baseline scores, subgroups or independent factor and subgroup-by-baseline interaction.

Adjusted mean of subgroups with 95% confidence intervals will be presented. Bonferroni pairwise adjusted comparison of means will be done when significant differences among the group is established.

All statistical analysis tables for PROMIS, AOS and FAOS will be will have the elements as presented in the template below.

Visit	Factor (or sub-factor X)	All Subjects (N=xx)	Group 1 (N=xx)	Group 2 (N=xx)
Pre-operative	N	XX	XX	XX
-	Mean $\pm$ SD	$xx.x \pm xx.x$	$xx.x \pm xx.x$	$xx.x \pm xx.x$
	1st Q, Median, 3rd Q	XX.X, XX.X, XX.X	XX.X, XX.X, XX.X	XX.X, XX.X, XX.X
	Min, Max	XX.X , XX.X	XX.X , XX.X	XX.X , XX.X
	Difference in means			XX.X
	p-value for mean difference*=0			X.XXX
Post-op Visit	Ν	XX	XX	XX
-	Mean $\pm$ SD	$xx.x \pm xx.x$	$xx.x \pm xx.x$	$xx.x \pm xx.x$
	1st Q, Median, 3rd Q	xx.x, xx.x, xx.x	XX.X, XX.X, XX.X	xx.x, xx.x, xx.x
	Min, Max	XX.X , XX.X	XX.X , XX.X	XX.X, XX.X
	p-value for change from baseline***	X.XXX	X.XXX	X.XXX
	Difference in group means			XX.X
	p-value for group difference**=0			X.XXX
	Adjusted mean $\pm$ se**		$xx.x \pm xx.x$	$xx.x \pm xx.x$
	95% CI for the Difference in Mean**			(xx.x , xx.x)
	Change from Baseline			
	N	XX	XX	XX
	Mean $\pm$ SD	$xx.x \pm xx.x$	$xx.x \pm xx.x$	$xx.x \pm xx.x$
	1st Q, Median, 3rd Q	xx.x, xx.x, xx.x	xx.x, xx.x, xx.x	xx.x, xx.x, xx.x
	Min, Max	XX.X , XX.X	XX.X , XX.X	XX.X, XX.X
	Difference in group means			XX.X
	Adjusted mean ± se**		$xx.x \pm xx.x$	$xx.x \pm xx.x$
	95% CI for the Difference in Mean**			(xx.x , xx.x)
	p-value for group mean difference=0**			X.XXX

Table 3	. Template	of statistical	tables for	PROMIS,	AOS and FAOS
---------	------------	----------------	------------	---------	--------------

Note: Results will be presented for each post-operative visit.

\*One-way analysis of variance for group difference. \*\*Results of ANCOVA, group variable as fixed effect and baseline as covariate, means adjusted for baseline.

\*\*\*t-test or Wilcoxon test p-value for two related samples.

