### **Missing Data**

Missing data will not be imputed. Patients who were missing data required for a given analysis will be excluded.

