## LISTING OF TABLES

Table	1.1	Subject Disposition
Table	1.2	All Protocol Deviations
Table	1.3	Demographics and Clinical Characteristics
Table	1.4	Medical History
Table	1.7	Surgical and Operative Information
Table	1.8	Additional Surgical Procedures Performed
Table	2.1	Life-table survivorship of INFINITY® Total Ankle System
Table	2.2.1	Ankle Osteoarthritis Score (AOS) by Instrumentation Type
Table	2.2.2	Ankle Osteoarthritis Score (AOS) Comparison by COFAS
Table	2.2.3	Ankle Osteoarthritis Score (AOS) by Disease Diagnosis
Table	2.2.4	Ankle Osteoarthritis Score (AOS) by Study Site
Table	2.2.5	Ankle Osteoarthritis Score (AOS) Comparison of Degenerative & Post-
Table	2.2.6	traumatic vs Inflammatory (RA) Ankle Osteoarthritis Score (AOS) Comparison by Degree of Valgus/Varus
		deformity
Table	2.2.7	Ankle Osteoarthritis Score (AOS) Comparison by Linear radiolucency
		(>2mm)
Table	2.2.8	Ankle Osteoarthritis Score (AOS) Comparison by Cystic Radiolucency
Table	2.3.1	(>5mm) PROMIS Global Health Score by Instrumentation Type
Table	2.3.2	PROMIS Global Health Score Comparison by COFAS
Table	2.3.3	PROMIS Global Health Score by Disease Diagnosis
Table	2.3.4	PROMIS Global Health Score by Study Site
Table	2.3.5	PROMIS Global Health Score Comparison of Degenerative & Post-traumatic
		vs Inflammatory (RA)
Table	2.3.6	PROMIS Global Health Score Comparison by Degree of Valgus/Varus
		deformity
Table	2.3.7	PROMIS Global Health Score Comparison by Linear radiolucency (>2mm)
Table	2.3.8	PROMIS Global Health Score Comparison by Cystic Radiolucency (>5mm)
Table	2.4.1	Foot and Ankle Outcome Score by Instrumentation Type
Table	2.4.2	Foot and Ankle Outcome Score Comparison by COFAS

Table	2.4.3	Foot and Ankle Outcome Score by Disease Diagnosis
Table	2.4.4	Foot and Ankle Outcome Score by Study Site
Table	2.4.5	Foot and Ankle Outcome Score Comparison of Degenerative & Post-
		traumatic vs Inflammatory (RA)
Table	2.4.6	Foot and Ankle Outcome Score Comparison by Degree of Valgus/Varus
		deformity
Table	2.4.7	Foot and Ankle Outcome Score Comparison by Linear radiolucency (>2mm)
Table	2.4.8	Foot and Ankle Outcome Score Comparison by Cystic Radiolucency
		(>5mm)
Table	2.5.1	Patient TAR satisfaction by visit and Instrumentation Type
Table	3.1	Radiographic Assessment by Visit
Table	3.2	Surgical Intervention by Visit
Table	4.1	Summary of Adverse Events – Treated Population
Table	4.2	Treatment Emergent Adverse Events
Table	4.3	Treatment Emergent Adverse events by visit

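### The SAP names Levene's test, which compares variances, as its test of equal regression slopes in the PROM subgroup ANCOVAs (minor correction)

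*SAP*

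**What the plan says.** Under Group Comparisons, the SAP plans an ANCOVA of each PROM by subgroup: "At each post-surgery visit, the patient reported outcome (PROMIS, AOS and FAOS) score and the change from baseline scores will be analyzed". It lists the terms: "The components of the ANCOVA model are: baseline scores, subgroups or independent factor and subgroup-by-baseline interaction". The output is described as follows: "Adjusted mean of subgroups with 95% confidence intervals will be presented". The double-asterisk footnote to Table 3 describes the same results more briefly: "Results of ANCOVA, group variable as fixed effect and baseline as covariate, means adjusted for baseline".

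Under Test of assumptions, normality is assigned to the Shapiro-Wilk test. The section then requires a common outcome-on-baseline relationship across subgroups and commits to checking it: "The regression slope of response factor on the covariate at each subgroup will be tested for equality". The sentence that follows names Levene's test for that purpose: "The Levene's test will be implemented to test the assumption of homogeneity of regression slope of response factor on the covariate at each subgroup". No other section names a slope test, no test is named for equality of variances as such, and neither section says that the interaction term is the slope test. The SAP does not say whether Levene's test is applied to raw values or to residuals, or what follows if the check fails.

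**The concern.** Equal slopes and equal variances are different ANCOVA conditions. Levene's test addresses only the second. It reacts to slopes indirectly, when a slope difference happens to change the spread of the quantity tested. A programmer who follows the section literally would run a check that does not answer the question it poses. It could report slopes as homogeneous when they are not, or as heterogeneous when only the spread differs.

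What is at stake is a wrong statement about an assumption behind the secondary PROM subgroup tables. Survivorship, the pre/post tests, satisfaction and safety do not use this check.

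**Working it through.** **Inputs.** From the SAP: 155 participants, eight subgroup tables for each of three PROMs (Listing of Tables; for example "Ankle Osteoarthritis Score (AOS) Comparison by COFAS"), and six post-operative visits. Missing data reduce the numbers: "Patients who were missing data required for a given analysis will be excluded". The documents give no slopes, SDs or subgroup sizes, and the protocol says that the sample size was not calculated statistically, so there is no plan figure to reproduce. Assumed here: baseline SD 18, residual SD 18 unless stated, and N = 155 or 100.

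**What Levene's test sees.** With slope b, the within-group variance is b² × 18² + 18² for the score and (b − 1)² × 18² + 18² for the change from baseline. For slopes 0.2 and 0.6:

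- Score: 0.04 × 324 + 324 = 337.0, and 0.36 × 324 + 324 = 440.6.
- Change: 0.64 × 324 + 324 = 531.4, and 0.16 × 324 + 324 = 375.8.

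The same slope difference makes one group more variable on the score and the other more variable on the change. With slopes +0.5 and −0.5 the score variances are equal, so Levene's test on the score has nothing to detect. Residuals from the separate-slopes model carry no trace of the slope difference.

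**Rejection rates** (5% level, 4000 replicates, mean-centred Levene; simulation standard error at most √(0.25/4000) = 0.8 points). The residual column uses the common-slope model.

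| Setting | Interaction F | Levene, score | Levene, change | Levene, residuals |
|---|---|---|---|---|
| 78/77, equal slopes and SDs | 5.0% | 5.0% | 5.3% | 5.0% |
| 78/77, slopes 0.3 v 0.5 | 23.1% | 9.2% | 11.1% | 4.9% |
| 78/77, slopes 0.2 v 0.6 | 68.0% | 18.6% | 29.3% | 4.2% |
| 50/50, slopes 0.3 v 0.5 | 15.8% | 7.1% | 8.9% | 4.6% |
| 50/50, slopes 0.2 v 0.6 | 49.1% | 14.3% | 20.2% | 4.6% |
| 78/77, equal slopes, SD 15 v 18 | 5.6% | 23.2% | 18.6% | 31.3% |
| 78/77, equal slopes, SD 12 v 20 | 5.6% | 92.0% | 78.1% | 98.2% |

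A separate simulation on a unit-SD scale (78/77, slopes +0.5 v −0.5) gave 100% for the interaction test. Levene's test gave 5.0% on the outcome, 2.3% on common-slope residuals and 5.2% on separate-slope residuals.

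**Score against change.** Subtracting baseline from the outcome lowers every slope by 1 and leaves slope differences and ANCOVA residuals unchanged. The interaction F test must therefore agree for score and change, and it did in all 84,000 data sets. Levene's test on raw values disagreed between the two in 42% of data sets at slopes 0.2 v 0.6 (78/77).

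**Limits of the interaction test.** Its power for slopes 0.3 v 0.5 is only 16% to 23%. With both sizes and variances unequal it is miscalibrated: at 125/30 with equal slopes it rejected in 14.4% (SD 12 v 20) or 0.5% (SD 20 v 12).

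**Number of checks.** PROMIS has 2 components, FAOS has 5 subscales, and AOS has a total with or without its 2 components. That is 2 + 5 + 1 = 8 to 2 + 5 + 3 = 10 scores. Over 8 tables and 6 visits: 8 × 8 × 6 = 384 to 10 × 8 × 6 = 480 interaction p-values. If all slopes were equal, 0.05 × 384 = 19.2 to 0.05 × 480 = 24 would fall below 0.05 by chance.

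**Text against footnote.** Power for a subgroup difference, without the interaction v with it at the overall mean baseline, with assumed sizes and effects and equal true slopes: 78/77, 80.1 v 80.1%; 125/30, 58.2 v 57.5%; 145/10, 75.4 v 72.0%; 150/5, 74.6 v 65.1%; nine sites of 45 down to 3, 75.1 v 71.1%. Conversely, when slopes, sizes and baseline means all differ (125/30, slopes 0.2 v 0.6, baseline means 50 v 60, true difference 0 at the overall mean baseline), the error rate is 9.9% without the interaction and 4.7% with it.

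**The case against.** The strongest reply is that little turns on this. The interaction is already among the model terms, so the right test comes from the planned fit. The section separately commits to testing the slopes, and its last sentence reads like two checks run together. Table 3 has no row for the check, and no analysis changes with its result. If the interaction stays in the reported model, equal slopes is not even an assumption of that model. This stands as an argument about severity. It does not remove the error: the sentence expressly assigns Levene's test to slopes, and nothing identifies the interaction as the slope test.

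It is also fair that every rejection rate rests on assumed values. The rates illustrate the mismatch; they do not measure harm in this trial.

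Three stronger readings are tempting and are not supported:

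- A reader might infer that the subgroup results are invalid. The SAP attaches no decision to the check, so only the statement about the assumption is wrong.
- A reader might call the model text and the Table 3 footnote contradictory. The footnote does not exclude the interaction and may be shorthand.
- A reader might conclude that the interaction should stay in every table at negligible cost. That holds with 30 or more per group, but the planned tables include study site (9 sites), four COFAS types and radiolucency groups that may be small. With assumed subgroups of 5 to 10, the loss is about 3 to 10 points of power.

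**Conclusion.** The SAP names the wrong test for slope equality. This follows from what Levene's test compares and needs no assumption about the data. Under the assumed values, the named check ranges from weak to blind for slope differences that the interaction test finds in about two thirds of data sets, and it rejects in most data sets when slopes are equal but SDs are 12 and 20.

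The correction is minor. It is confined to secondary PROM subgroup comparisons, and no stated decision depends on it. The replacement also has limits: low power for small slope differences, and miscalibration when sizes and variances are both unequal. Its p-values are descriptive and should be read beside a variance check. The difference between the model text and the Table 3 footnote is a separate ambiguity to be reconciled.

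**What to change.** Replace the Levene sentence under Test of assumptions with:

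*Equality of regression slopes will be tested with the subgroup-by-baseline interaction F test from the ANCOVA model under Group Comparisons. Levene's test will be applied to the residuals of that model to assess equality of variances only.*

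Show the residual Levene result beside the interaction p-value, and label the interaction p-values as descriptive. One interaction p-value serves both score and change.

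Separately, make the Group Comparisons text and the Table 3 footnote name the same reported model. Either choice is open to the sponsor. If the interaction is kept, state the baseline value at which subgroups are compared and accept the power loss in very small subgroups. If it is left out, state that it is fitted for the slope check only.

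The cost is a few sentences, one footnote, a place to show the two p-values and a small program change. No new data are needed. The price is 384 to 480 further p-values, of which about 19 to 24 would fall below 0.05 by chance if all slopes were equal.

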### **Patient Disposition and Accounting**

A table to account for the status of all enrolled subjects will be constructed to include frequency of subject non-completion, subject retention rates and deaths at the 10+ years follow-up period. The reasons for subject non-completion and causes of death will also be summarized. The accounting table will also include, at each follow-up time, the number of subjects followed-up who have complete data and the number of subjects who have any data.

The patient disposition summaries discussed above will also be presented for patients implanted per the "standard instrumentation" and for patients implanted per the "approved additional instrumentation".

### **Demographics and Baseline Clinical Characteristics**

Demographics and clinical data including gender, age, race, height, weight, BMI, smoking status, affected foot or ankle, foot or ankle to be treated, will be summarized with descriptive statistics (min, max, mean, median, and standard deviation).

Subject's pre-operative end-stage arthritis radiograph results will be summarized based on the Canadian Orthopaedic Foot and Ankle Society (COFAS) categories as follows:

Type 1: Isolated ankle arthritis

Type 2: Ankle arthritis with intra-articular varus or valgus deformity or a tight heel cord, or both

 intra-articular ankle varus or valgus alignment was defined as the angle of the proximal talar surface (talar tilt) to the lateral border of the tibia in the distal diaphysis and metaphyseal region more than 10 degrees on the AP weightbearing ankle views

Type 3: Ankle arthritis with hindfoot deformity, tibial malunion, midfoot abductus or adductus, supinated midfoot, plantar flexed first ray, etc.

hindfoot deformity defined as the angle between the lateral border of the calcaneus
 04 October 2021

and the long axis of the tibia on the AP view of the ankle (varus more than 5 degrees, valgus more than 10 degrees)

- Tibial deformity defined as an angulation between the lateral border of the tibia more than 10 degrees on the AP view of the ankle, or
- patient has required staged surgical deformity as part of the management of the ankle arthritis (within 18 months of TAR), this should be considered a type 3

Type 4: Types 1, 2, and 3 plus subtalar, calcaneocuboid, or talonavicular arthritis

The post-operative radiographic evaluations are done to report migration, loosening, subsidence of the device, any osteolysis and cyst formation.

### Survivorship of INFINITY® Total Ankle System

Survivorship of INFINITY® Total Ankle System will be based on secondary surgical intervention performed on the original implant. The Kaplan Meier survivorship method and life table analysis will be employed. Time to surgical intervention due to implant failure will be the survivorship endpoint of INFINITY® Total Ankle System. In addition, time to reoperation to exchange or remove any part of the INFINITY® Total Ankle System or surgical intervention due to failure of the implant as survivorship endpoint will also be analyzed. Subjects who did not undergo revision or reoperation due to implant failure at the time of reporting will be censored at the last follow-up. The Kaplan Meier survival curve with the 95% Confidence Interval will be constructed.

Year since	Number	Number of	Lost	Survival	95%
implantation	at start	failed implant		Rate	Confidence
					Interval
0-1	1		I		
1-2					
2-3					
3-4					
4-5					
5-6					
6-7					
7-8					
8-9					
9-10					

Table . Kaplan-Meier life-table survival of INFINITY® Total Ankle System.

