## **Device** Failure

Subjects will be considered a treatment failure, and will be withdrawn from the study if any sections of the device (tibial or talar metal components) have been removed at any time during their participation. This should be reported onto the adverse event form. In addition, any surgical intervention during study participation that relates to their total ankle replacement will be reported on the surgical intervention case report form.

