#### 2. Subsequent secondary surgical interventions

Adverse events that lead to secondary surgical intervention will be summarized, categorized by type of surgical intervention performed, namely: reoperation, reoperation with removal of implanted components, other interventions. The primary reason for the surgical intervention will be categorized as: implant failure, deep infection, aseptic loosening, subsidence, wound healing

Page 17 of 23

problems, bone fracture, non-union and other reasons will also be tabulated in the same manner.

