### 2. Report Timing of survivorship assessment

There will be two timepoints to assess and report survivorship, at the 5th (intermediate survivorship assessment) and 10th (long-term survivorship assessment) year follow-up.

At the intermediate assessment of survivorship (5th year follow-up), only patients with follow-up scores obtained at least four years after surgery will be included in the analysis. Patients who underwent reoperation or revision surgery with in four years of surgery will not be excluded. At the final assessment of survivorship (10th year follow-up), only patients with follow-up scores obtained at least eight years after surgery will be included in the analysis. Patients who underwent reoperation or revision surgery will be included in the analysis. Patients who underwent reoperation or revision surgery will be included in the analysis.

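### The primary 10-year survivorship event is not fixed: the SAP gives two different bases for it, and the one it names as the endpoint rests on an undefined term, implant failure

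*SAP*

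**What the plan says.** The protocol (Primary and Secondary Endpoints) defines the primary endpoint as a 10-year Kaplan-Meier survivorship rate and names no event. Its Device Failure section treats a subject as a treatment failure "if any sections of the device (tibial or talar metal components) have been removed at any time during their participation", with no limit on reason. It does not call this the survivorship event.

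The SAP section on survivorship of the system makes four statements in turn:

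- Survivorship "will be based on secondary surgical intervention performed on the original implant".
- "Time to surgical intervention due to implant failure will be the survivorship endpoint".
- In addition, a second endpoint is analysed: "time to reoperation to exchange or remove any part of the INFINITY" system, or surgery because the implant failed.
- "Subjects who did not undergo revision or reoperation due to implant failure at the time of reporting will be censored at the last follow-up". This is the only censoring rule for time-to-event subjects, and it follows both endpoints.

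The SAP's Effectiveness objectives repeat the term implant failure without defining it. Under Subsequent secondary surgical interventions, a safety summary, the primary reason for surgery is "categorized as: implant failure, deep infection, aseptic loosening, subsidence, wound healing" problems and further reasons. The same summary has a category for "reoperation with removal of implanted components". On the final survivorship assessment, the report-timing section says: "Patients who underwent reoperation or revision surgery will be included in the analysis". At year 5 it likewise does not exclude patients reoperated or revised within four years. Table 2.1 and Figure 1 name no event, and Figure 2 is titled as time to implant failure.

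**The concern.** A Kaplan-Meier estimate means nothing until the event is stated. Here the reader meets a reason-free basis and a reason-dependent endpoint in the same paragraph, and the reason is an undefined term. Two analysts could each follow the SAP and report different 10-year rates under the same table title. The narrowest reading counts the fewest events and so favours the device. A curve restricted to one cause of failure can be a legitimate target, but the SAP does not say that this is intended, and it labels the life table simply as survival of the system. Unless the event is fixed in advance, the choice can be made after the data have been seen.

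**Working it through.** **There is no plan figure to reproduce.** The protocol states that the sample size was not calculated statistically. Neither document gives an expected survival rate, event count or loss rate. The check is therefore a comparison of texts, followed by an illustration of size.

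**Step 1: one case under each statement.** Take a tibial tray removed with deep infection as the primary reason.

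| Statement | Is it an event? |
|---|---|
| SAP opening sentence (any secondary surgery on the implant) | Yes |
| SAP named endpoint (surgery due to implant failure) | Undetermined; no if the safety reason codes decide, yes if the term is read broadly |
| SAP additional endpoint (any part exchanged or removed, or surgery due to failure) | Yes |
| Protocol Device Failure | Treatment failure; not stated whether it is a survivorship event |

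An exchange of the polyethylene insert alone is an event for the additional endpoint but is not named in Device Failure, which refers to the metal components.

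**Step 2: the censoring sentence.** The qualifier about implant failure may attach only to reoperation, or to both revision and reoperation. On the second reading, the subject above is censored by the rule although the additional endpoint counts that subject as an event. On the first reading the conflict disappears only if every exchange or removal is called a revision, another term the SAP leaves undefined.

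**Step 3: outputs.** One life table and two figures are listed. Nothing says which endpoint each one shows.

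**Step 4: possible size (assumed rates).** Let S be the true 10-year freedom from removal and s the share of removals counted as implant failure. With proportional cause-specific hazards, a curve that censors the rest estimates S^s.

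| S | s = 1 | s = 1/2 | s = 1/3 |
|---|---|---|---|
| 95% | 95.0% | 97.5% | 98.3% |
| 90% | 90.0% | 94.9% | 96.5% |
| 85% | 85.0% | 92.2% | 94.7% |

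For example, 0.90^(1/2) = 0.949 and 0.90^(1/3) = 0.965. The half-count gap at S = 90% is 94.9 − 90.0 = 4.9 points.

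A discrete check used 155 implants and 16 removals, spaced half a year apart from 0.5 to 8 years, with everyone else followed to year 10. Kaplan-Meier gives 89.7% if all 16 are events and 94.7% if every second one is.

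**Step 5: precision at S = 90%, N = 155 (the number enrolled), one implant per patient, no loss.**

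- All-removal estimate: sqrt(0.90 × 0.10 / 155) = 0.024, or 2.4 points.
- Half-count gap: the two curves come from the same subjects, so the gap has its own standard error. The variance of the total cumulative hazard is about 0.10 / (155 × 0.90) = 0.000717, half of it (0.000358) from each cause. By the delta method, the variance of the gap is [(0.949 − 0.900)² + 0.90²] × 0.000358 = 0.00029. The standard error is 0.017, or 1.7 points.

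**The case against.** **A reader might infer that the SAP does censor removals for infection, loosening and subsidence.** The documents do not support that. The reason codes belong to a safety tabulation, and the survivorship section does not refer to them. Keeping reoperated and revised patients at years 5 and 10, when others with short follow-up are left out, fits a reading in which they are events. That evidence is real but not decisive: the report-timing section says such patients stay in the analysis, not how they are classified.

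**A reader might also count four conflicting definitions.** That is too many. The second SAP endpoint is openly additional and contradicts nothing. Device Failure concerns treatment failure and withdrawal. The opening SAP sentence can be taken as a general basis that the next endpoint sentence narrows. What stands is an undefined term in the named endpoint, an unreconciled opening sentence, an ambiguous censoring rule and unlabelled outputs.

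**The additional endpoint already captures removals for any reason.** It does, and this limits the harm. But it is not the endpoint that the SAP names first, one reading of the censoring rule cuts into it, and no listed output is assigned to it.

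**The study is single-arm and observational, with no performance goal or comparator.** That is correct, so no pass/fail decision turns on this point.

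**Conclusion.** The concern holds in this form: the event for the primary endpoint is not fixed, and the SAP followed as written permits different values of the 10-year rate. Exclusion of infection, loosening and subsidence removals from the first-named curve is a conditional consequence, not something the SAP states.

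The true size cannot be known from the documents. At an assumed 90% freedom from removal with half of removals counted, the reported figure rises by 4.9 points (standard error of the gap about 1.7, against 2.4 for the all-removal estimate). At 95% and 85% the half-count gap is 2.5 and 7.2 points. It is zero if every removal counts. These figures assume proportional hazards; the standard errors also assume one implant per patient and no loss to follow-up.

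This should be corrected before the survivorship analysis, because it affects the primary endpoint and the narrow reading favours the device.

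**What to change.** In the SAP survivorship section, state one primary event that does not depend on the coded reason for surgery, and reconcile it with that section's opening sentence and with the protocol's Device Failure section. The existing additional endpoint already has this form for removals, and it keeps failure-related surgery without removal. Defining the primary event as removal alone would drop that surgery.

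Also:

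- The sponsor should state whether insert-only exchange counts in the primary event.
- If surgery due to implant failure is kept, define the term and label the analysis as cause-specific.
- For each endpoint, censor only subjects without that endpoint's event.
- In the report-timing section, say that the retained reoperated and revised patients are classified by the same rule.
- Use the safety reason codes only to tabulate causes.
- Name the event in Table 2.1 and in Figures 1 and 2.

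The cost is SAP wording and one or two extra life tables, and the survival figure may be less favourable. The protocol already requires removals to be reported on the adverse event form and related surgery on the surgical intervention form. The content of those forms is not in the documents, so the sponsor should check that they separate metal-component removal from insert exchange.

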## Primary and Secondary Endpoints

The primary endpoint is a survivorship rate at 10 years as defined with a Kaplan Meier survivorship analysis. Secondary endpoints identify, assess and compare functional improvements or deviations collected through investigator observation and patient self-reporting, and include:

• Identification and assessment of the implant through radiographic assessment for component loosening and/or subsidence, any osteolysis and/or cyst formation early and throughout the lifetime of the implant.

- Comparison of improvements in self-reported physical, mental, and social health measures from pre-op through 10 years post operatively; assessed by PROMIS®.
- Comparison of pain and functional improvement from pre-op through 10 years in the AOS which is a visual analogue scale specifically designed as a modification of the Foot function Index.
- Comparison of the improvements in patient/physician reported function scores from pre-op through 10 years post-operatively, assessed by FAOS scores.
- Compare satisfaction of total ankle replacement post operatively utilizing a four point scale
- Identification and reporting on the safety of the implant in terms of complications and adverse events.

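### Survivorship: deaths without failure have no stated handling, and the only cumulative estimates planned are Kaplan-Meier, whose complement overstates the share of patients who will have a failure

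*SAP*

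**What the plan says.** The protocol (Primary and Secondary Endpoints) fixes the method: "The primary endpoint is a survivorship rate at 10 years as defined with a Kaplan Meier survivorship analysis".

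The SAP (Survivorship of INFINITY® Total Ankle System) defines two events, both surgical. The first is: "Time to surgical intervention due to implant failure will be the survivorship endpoint of INFINITY® Total Ankle System". The second is broader and adds "time to reoperation to exchange or remove any part of the INFINITY® Total Ankle System". Death is part of neither. The censoring rule is: "Subjects who did not undergo revision or reoperation due to implant failure at the time of reporting will be censored at the last follow-up". The life table in the same section ("Kaplan-Meier life-table survival of INFINITY® Total Ankle System") has two ways out of the risk set, failed implant and Lost.

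The SAP (Other considerations, item 2, on the timing of survivorship reports) sets the population for the 10-year assessment: "only patients with follow-up scores obtained at least eight years after surgery will be included in the analysis". It then makes an exception: "Patients who underwent reoperation or revision surgery will be included in the analysis". The 5-year assessment has a parallel rule with a four-year threshold. The SAP's General Considerations, by contrast, put all implanted subjects in the analysis.

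Deaths are counted elsewhere. The SAP (Patient Disposition and Accounting) plans "frequency of subject non-completion, subject retention rates and deaths at the 10+ years follow-up period", together with causes of death and reasons for non-completion. Failures are also counted outside the Kaplan-Meier analysis, in the section on secondary surgical interventions (by type and by primary reason) and in Table 3.2 of the table list.

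Neither document mentions competing events or a cumulative incidence estimate.

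**The concern.** A patient who dies with the implant in place cannot later be revised. Censoring that patient treats revision as still possible, so one minus the Kaplan-Meier estimate describes failure in the absence of death. This is a reasonable way to describe an implant. It is not the probability that a patient has a failure within 10 years, and it exceeds that probability whenever any patient dies first. The SAP does not say which of the two quantities it is estimating and plans no estimate of the second.

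Two further points follow. The life table does not separate death from true loss within each year, although true loss is the part of the censoring that can bias the net estimate. And the survivorship section and the report-timing section treat the same patients differently: one keeps an unrevised early death until last follow-up, the other removes that patient from the denominator altogether.

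**Working it through.** **Inputs.** The documents give 155 enrolled subjects and a 10-year horizon. They give no survival target, failure rate, mortality or age distribution, and the protocol says the sample size was not derived statistically. There is therefore no planned figure to reproduce. Assumed: 10-year net failure F of 5% to 20%, 10-year mortality M of 5% to 40%, constant and independent hazards, no other loss to follow-up, and every reoperation counted as a failure.

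**Step 1: deaths censored, all implanted subjects analysed.** Hazards are l = −ln(1−F)/10 and m = −ln(1−M)/10. Then 1−KM = F, and the cumulative incidence with death competing is CIF = l/(l+m) × [1 − exp(−10(l+m))].

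For F = 10% and M = 20%:
- l = 0.01054, m = 0.02231, l+m = 0.03285
- exp(−0.3285) = 0.90 × 0.80 = 0.72
- CIF = 0.3207 × 0.28 = 8.98%
- excess of 1−KM: 10.00 − 8.98 = 1.02 points, or 15.5 against 13.9 patients in 155

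A simulation of 1,000,000 subjects gave a CIF of 9.02%.

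**Step 2: the report-timing rule applied as written.** Keep all failures and only those unrevised subjects still followed at year 8. Same F and M:
- fraction kept = failures 0.0898 + deaths in years 8–10 0.0332 + alive and unrevised at year 10 0.7200 = 0.8430, about 131 of 155
- failures by year 8 = 0.3207 × (1 − exp(−0.2628)) = 0.0741
- KM at year 8 = 1 − 0.0741/0.8430 = 0.9121
- KM at year 10 = 0.9121 × exp(−2 × 0.01054) = 0.8931
- 1−KM = 10.69%, which is 1.71 points above the CIF: 1.02 from censoring and 0.69 from the exclusion

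**Step 3: range** (differences taken before rounding).

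| F | M | CIF | Excess of 1−KM, points | Ratio F/CIF | 1−KM with exclusion | Excess with exclusion, points |
|---|---|---|---|---|---|---|
| 5% | 5% | 4.88% | 0.12 | 1.026 | 5.08% | 0.20 |
| 5% | 40% | 3.92% | 1.08 | 1.274 | 5.90% | 1.97 |
| 10% | 10% | 9.50% | 0.50 | 1.053 | 10.32% | 0.82 |
| 10% | 20% | 8.98% | 1.02 | 1.114 | 10.69% | 1.71 |
| 10% | 30% | 8.44% | 1.56 | 1.185 | 11.15% | 2.71 |
| 20% | 20% | 18.00% | 2.00 | 1.111 | 21.26% | 3.26 |
| 20% | 40% | 15.81% | 4.19 | 1.265 | 23.05% | 7.24 |

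**Step 4: size against sampling error.** At F = 10%, the approximate 95% half-width with 155 subjects and no censoring is 1.96 × √(0.10 × 0.90/155) = 4.7 points.

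**Step 5: can the planned counts stand in for a cumulative incidence?** Add an assumed 20% loss over 10 years, with hazard g = −ln(0.8)/10 = 0.02231. The expected crude share with an observed failure is l/(l+m+g) × [1 − exp(−10(l+m+g))] = 0.1910 × 0.424 = 8.10%, against a CIF of 8.98%. Crude counts miss failures after loss, so they do not give the 10-year risk.

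**The case against.** The strongest reply is that the study is about the implant. The objective is implant survivorship, the protocol names Kaplan-Meier, and the SAP reports a survival rate and nowhere offers its complement as a patient's risk. That stands, and it defeats any proposal to replace Kaplan-Meier. It does not answer the request for a stated rule on death and a companion estimate.

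Several stronger readings are tempting, and the documents do not support them:
- A reader might infer that Kaplan-Meier supplies the only failure figure. It does not. The life table counts failed implants, secondary interventions are tabulated by type and reason, and Table 3.2 reports them by visit. What is absent is any other cumulative time-to-event estimate.
- A reader might infer that deaths are counted under Lost. The SAP does not say so. That is a guess from the column layout, and the report-timing rule removes most early deaths before they could be entered.
- A reader might infer that deaths are concealed. They are not. The disposition table reports deaths, causes and reasons for non-completion. Only the yearly split within the life table is missing.
- A reader might infer a large bias. The documents give no mortality and admit patients from age 21. At low mortality the excess is a fraction of a point, and in the central scenario it is well inside the sampling error.

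**Conclusion.** The point holds as a low-cost improvement; it does not invalidate the primary analysis. The SAP gives no rule for death, its two survivorship passages conflict on unrevised patients who die early, and both planned cumulative estimates are Kaplan-Meier. The complement of either exceeds the share of patients who will have a failure if any die first. The direction is certain; the size is not. Under the assumed ranges it is about 0.1 to 4.2 points with deaths censored in all implanted subjects, and 0.2 to 7.2 points if the eight-year restriction is applied literally. At 10% failure and 20% mortality the figures are 1.0 and 1.7 points. All sizes rest on constant, independent hazards and on rates that are not in the documents.

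**What to change.** Keep the Kaplan-Meier rate as primary and make four changes in the SAP.

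1. Reconcile the survivorship section with the report-timing section so that both assessments use all implanted subjects, without the four-year and eight-year follow-up conditions.
2. State that deaths without prior failure are censored at the date of death for Kaplan-Meier, not at the last visit. Scheduled visits are up to three years apart, so the choice affects the risk set.
3. Add the Aalen-Johansen cumulative incidence of failure, with death as a competing event, with 95% confidence intervals at 5 and 10 years on the same population. Label the Kaplan-Meier figure as net implant survivorship and this one as the patient's risk of failure.
4. Split the Lost column into died with implant in place, and lost or withdrawn.

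The cost is some SAP wording, one extra estimate and one extra column. Deaths and causes are already to be summarised; the sponsor should confirm that dates of death are recorded. The downside is that two figures must be explained side by side. The primary method does not change, although its value may once early deaths are no longer excluded.
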